6.6.2 Safety data and other data

In general, missing data will not be imputed and only observed values will be analyzed.

6.6.3 AE dates and times

Missing or incomplete AE dates will be imputed according to “Handling of missing and incomplete AE dates” [\(3\)](#).

[REDACTED]

[REDACTED]

6.6.5 Blood serum and plasma biomarker data

Missing blood serum and plasma biomarker data will not be imputed. Values below the limit of quantification (BLQ) of the assay will be imputed to BLQ/2. Values above the limit of quantification (ALQ) will be imputed to the ALQ.

6.7 BASELINE, TIME WINDOWS AND CALCULATED VISITS

For all analyses, baseline refers to the baseline value in the 1407-0030 study.

For laboratory safety measurements, the last measurements taken prior to the intake of BI 730357 or placebo will be considered as baseline.

In general, measurements reported with a date only (and no time) and taken on the day of first administration of trial treatment will also be considered pre-treatment values.

The visit schedule with accompanying details can be found in Flow Chart in the CTP. Measurements taken after start of treatment will be considered either on- or off-treatment values based on definition in [Table 6.1: 1](#).

On-treatment measurements for EOT and EOS visit for early discontinued patients will be allocated to visits by means of time windows with the limit between adjacent windows half-way between the planned dates for the visits; the middle day is counted to the window of the later visit. Mutually exclusive relative day windows are defined below to provide derived visits that correspond to the post-baseline time points. For example, Visit 2 is planned on Day 84 and Visit 3 is planned on Day 168. Therefore, the window of Visit 2 reaches until Day 125 while the window of Visit 3 starts on Day 126. The visit schedule with corresponding windows is given in the following table.

Table 6.7: 1 Time windows for patient visits

Window No.	Window label	Nominal visit	Nominal day	Interval
1	Day 1	Visit 1	1	N/A
2	Week 12	Visit 2	84	[2, 125]
3	Week 24	Visit 3	168	[126, 209]
4	Week 36	Visit 4	252	[210, 293]
5	Week 48	Visit 5	336	[294, 377]
6	Week 60	Visit 6	420	[378, 461]
7	Week 72	Visit 7	504	[462, 545]
8	Week 84	Visit 8	588	[546, 629]
9	Week 96	Visit 9	672	[630, 713]
10	Week 108	Visit 10	756	[714, 797]
11	Week 120	Visit 11	840	[798, 881]
12	Week 132	Visit 12	924	[882, 965]
13	Week 144	Visit 13	1008	[966, 1049]
14	Week 156	Visit 14	1092	[1050, 1133]
15	Week 168	Visit 15	1176	[1134, 1217]
16	Week 180	Visit 16	1260	[1218, 1301]
17	Week 192	Visit 17	1344	[1302, 1385]
18	Week 204	Visit 18	1428	[1386, 1469]
19	Week 216	Visit 19	1512	[1470, 1553]
20	Week 228	Visit 20	1596	[1554, 1637]
21	Week 240	Visit 21	1680	[1638, 1721]
23	Week 252	Visit 22	1764	[1722, 1805]
24	Week 264	Visit 23	1848	[1806, 1889]
25	Week 276	Visit 24	1932	[1890, 1973]
26	Week 288	EOT	2016	[1974, 2029]
27	Week 292	EOS	2044	[2030, ∞]

If there are multiple values for an efficacy endpoint in one window (visit), use the one from scheduled visit. If value from scheduled visit is not present, the visit closest to the nominal day will be selected for assessing endpoints at a particular visit and for by-visit displays. If the visits are equidistant from the nominal day, then the earlier visit will be selected. All measured values will be stored in analysis datasets.

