All patients entering the extension trial are to be assigned at Visit 1 to receive openlabel treatment with 400 mg q.d. (fed), the anticipated therapeutic BI 730357 dose. Refer to Figure 3.1: 2.

It is expected that Visit 1 of trial 1407-0005 will be performed on the same day of the EOT Visit of trial 1407-0030 in both patient groups. In the event that patients completing Part 2 of trial 1407-0030 are not able to be entered immediately into the extension trial due to administrative reasons (e.g., pending protocol approval, availability of trial medication), Visit 1 of the extension trial may be delayed for no more than 16 weeks. In the event of a delay, the CTM should be consulted and refer to the Flow Chart for procedures to be conducted.

The treatment period is this trial will be approximately 6 years.

[figure not shown]

Figure 3.1: 1 Trial 1407-0005 dose assignment/reassignment for patients entering from Part 1 of trial 1407-0030

[figure not shown]

Figure 3.1: 2 Trial 1407-0005 dose assignment for patients entering from Part 2 and continuing from Part 1 of trial 1407-0030

Page 28 of 84

Clinical Trial Protocol

Dose selection at Week 12 is based on the safety and tolerability data from the SRD Trial 1407.1 and the MRD Trial 1407-0002, and will be contingent on DMC evaluation of all available data from Phase II trial 1407-0030. For patients entering from Part 1 of trial 1407-0030, if an unacceptable risk regarding the safety of the 200 mg dose level is reported by the DMC, the open label BI 730357 dose assignments beginning at Week 12, as shown in Figure 3.1: 1, is to be altered to assign all patients to the 100 mg *q.d.* dose group. For additional

details and logistics, refer to Section 8.7. Refer to Section 4.1.2 for dose selection rationale.

All patients entering from Part 2 of trial 1407-0030 are to receive the 400 mg q.d. dose, as long as no unacceptable risks are identified during Part 2 of trial 1407-0030. Once Part 2 patients begin enrolling in this trial, existing patients receiving 100 mg q.d. in this trial will be given the option to titrate up to the 200 mg q.d. dose, if the investigator determines that the patients may benefit from the higher dose.

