3.2 DISCUSSION OF TRIAL DESIGN, INCLUDING THE CHOICE OF CONTROL GROUP(S)

Trial 1407-0005 is designed as a long-term extension clinical trial, and is expected to generate additional safety information to support registration submissions. Therefore, the primary endpoint is focused on safety. All patients who complete treatment with BI 730357 or placebo in the preceding Trial 1407-0030 and achieve a PASI50 response at Week 24 of that trial will be invited to participate to receive long-term treatment. Our goal in this study is to obtain additional safety, tolerability and efficacy data following long-term drug administration

For patients entering the extension trial from Part 1 of trial 1407-0030, the 12-week double blind treatment period (refer to Section 3.1) is intended to maintain the blind of the preceding trial while collecting additional data for the doses allocated at EOT in the preceding trial. After DMC review of all available safety data from 1407-0030 (refer to Section 8.7), the dose levels selected for the open label period of the extension trial will be confirmed and the long-term assessment of the 100 mg *q.d.* and 200 mg *q.d.* dose groups will begin at Visit 2/Week 12 (refer to Section 3.1). Visit 2.1 will be conducted by telephone 2 weeks after this transition as a precaution to monitor patient safety. Trial 1407-0005 may include placebo patients who have achieved a PASI 75 at Week 12 of 1407-0030 and a PASI50 at Week 24 of 1407-0030. Patients in this category that have meet these efficacy criteria would also need to be satisfied with their blinded treatment allocation at Week 24 of trial 1407-0030 and therefore selected to continue treatment by participating in the extension study. These patients will begin active treatment of 100 mg BI 730357 at Visit2/Week 12 of the extension study.

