Based on safety and efficacy data from Part 1, Part 2 of trial 1407-0030 extends dose ranging of BI 730357 to 400 mg q.d. and 200 mg b.i.d., to be administered under fed conditions. Given that PoC efficacy has been demonstrated in Part 1 of trial 1407-0030, in the second patient group, patients are to be considered eligible to participate in 1407-0005 upon completing the trial 1407-0030 Week 12 end-of-treatment visit with \geq 50% improvement in PASI50 or perceived patient improvement, at the discretion of the Investigator. Furthermore, given that patients in this group are to receive long-term BI 730357 at a substantially higher dose than in those in the first group, in the interest of safety, patients are to be considered

Page 29 of 84

eligible only if also without ongoing AEs consistent with intolerance of trial medication (including gastric intolerance), that in the opinion of the investigator would compromise the safety of the patient.

. Visits 1.1, 1.2 and 1.3 will be conducted in person for these patients to monitor patient safety, particularly as placebo patients may continue into this trial and receive active drug.

As a trial with an open label period, we realize that no powered or controlled analysis can be done. However, we will be able to evaluate initial tendencies and at the same time permit our early study participants an opportunity to maintain access to a therapy that has the potential to have clinical benefit.

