4.1.3 Method of assigning patients to treatment groups

For patients entering from Part 1 of trial 1407-0030, during visit 1, eligible patients will continue to receive their treatment allocation of BI 730357 received in the preceding study, in a blinded fashion, via Interactive Response Technology (IRT). Upon completion of Visit 2/Week 12 the patients in this extension study will be assigned to an open label BI 730357 dose, via IRT (refer to Section 3.1).

Patients entering from Part 2 of trial 1407-0030 will all be assigned to open label BI 730357 400 mg q.d.

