7.7 EXTENT OF EXPOSURE

Exposure will be presented as total days on treatment and total study medication intake assessed by actual treatment received. For example, a Placebo patient that switches to BI 730357 100 mg at Week 12 should have 12 weeks of exposure under the Placebo column and their number of days on BI 730357 100 mg under BI 730357 100 mg column.

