7.8.2 Laboratory data

The analyses of laboratory data will be descriptive in nature and will be based on BI standards [\(6\)](#). The number and percent of patients with possibly clinically significant on treatment abnormalities as identified by use of clinically significant ranges for each laboratory parameter collected will be presented. The patients from both parts of 1407-0030 with possibly clinically significant abnormalities will be identified by actual treatment received at study entry.

Each laboratory value will be graded using the RCTC (version 2.0) grading of laboratory abnormalities. A summary table of the baseline grade compared with the last available on treatment grade will display the number and percent of each type of transition in grade by laboratory parameter within each treatment period and treatment group. A second table will show the number and percent of patients with each type of transition from baseline to their worst on-treatment grade.

A graphical summary highlighting potential cases of Hy's Law by actual treatment received at study entry will be presented. The maximum on-treatment values of total bilirubin and ALT will be plotted each on a scale as multiples of the upper limit of normal. The figure will show areas that meet the criteria of cholestasis (total bilirubin $> 2 \times$ ULN), Temple's corollary (ALT $> 3 \times$ ULN) and Hy's Law as the combination of these two factors. A similar figure using maximum AST values in place of ALT will be constructed. An accompanying listing will show by sample date and study day the full course of the total bilirubin, ALT, AST and alkaline phosphatase values for patients whose total bilirubin are $> 2 \times$ ULN or AST or ALT values $> 3 \times$ ULN at any time during the study (all treatment periods). The listing will indicate where the value meets the criteria, either falling in the cholestasis range, that for Temple's corollary or where the combination meets that for Hy's Law itself.

Laboratory measurements taken up to the residual effect period of 7 days after the last administration of study drug will be considered as on-treatment.

Study visits will be presented by the Visit labels in [Table 6.7:1](#).

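### For Part 2 patients who took placebo in 1407-0030, the laboratory baseline lies about 12 to 28 weeks before their first BI 730357 dose, so the grade-shift tables can show pre-drug changes as changes on 400 mg

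*SAP*

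**What the plan says.** SAP 6.7 opens with a general rule, which protocol 7.3 also contains: "For all analyses, baseline refers to the baseline value in the 1407-0030 study". It then adds a rule for laboratory data: "For laboratory safety measurements, the last measurements taken prior to the intake of BI 730357 or placebo will be considered as baseline". The laboratory sentence does not say which trial's intake is meant. No second baseline is defined for the start of BI 730357.

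Former placebo patients are expected in Part 2. Protocol 3.2 explains the in-person Visits 1.1 to 1.3 as a safety measure, "particularly as placebo patients may continue into this trial and receive active drug". Protocol 4.1.3 gives the treatment: "Patients entering from Part 2 of trial 1407-0030 will all be assigned to open label BI 730357 400 mg q.d". Entry need not be immediate. For Part 2 patients with an administrative obstacle, protocol 3.1 says: "Visit 1 of the extension trial may be delayed for no more than 16 weeks".

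The baseline is used in SAP 7.8.2, which plans "A summary table of the baseline grade compared with the last available on treatment grade" by treatment period and treatment group, and a second table from baseline to worst on-treatment grade. SAP 6.1 combines Part 1 and Part 2 patients for laboratory outputs and defines no former-placebo group for them.

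**The concern.** A shift table under a dose heading is read as showing what happened to laboratory values on that dose. This works for patients who took BI 730357 from the start of 1407-0030, because their baseline is the last drug-free value. For a Part 2 former placebo patient, the same rule puts a placebo period, and possibly an untreated gap, between the reference value and the first dose.

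Two errors follow:

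- A grade change that arose before exposure and is still present in an on-treatment sample is tabulated as a transition on 400 mg.
- An abnormality present at the old baseline that had resolved before Visit 1 and then returned on drug is tabulated as no change.

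These are the newly exposed patients for whom the protocol added early safety visits. A nearer pre-dose sample exists and the rule passes over it.

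**Working it through.** The plan gives no figure to reproduce. The check follows the baseline rule through the visit schedule and the outputs.

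**Inputs from the documents**

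- Part 2 treatment in 1407-0030 ends at Week 12 (protocol 3.1 and 3.3.2).
- Maximum entry delay for Part 2 is 16 weeks (protocol 3.1; SAP 6.1).
- First BI 730357 dose of a Part 2 former placebo patient is at Visit 1 (protocol 3.1 and 4.1.3).
- Part 2 enters up to approximately 90 patients (protocol 3.1). The number formerly on placebo is not given.
- For any Part 1 former placebo patient, placebo runs 24 weeks in 1407-0030 and 12 weeks here (protocol 3.1 and 3.2). The synopsis plans 0 to 20 such patients.

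**Time from laboratory baseline to first BI 730357 dose**

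- Part 2, same-day entry: 12 weeks.
- Part 2, maximum delay: 12 + 16 = 28 weeks.
- Part 1, if any: 24 + 12 = 36 weeks.

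**Which changes are counted.** On-treatment values begin with the first dose in this trial (SAP Table 6.1: 1). A pre-drug change enters the worst-grade table if it is still present in one on-treatment sample; the first is scheduled at Week 2 for Part 2. It enters the last-grade table only if it is still present in the last sample of the period shown. A change that resolved before the first on-treatment sample is not counted.

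**Illustration of size.** The rates are assumptions and are not in the documents. If lasting grade shifts in one laboratory parameter arise at rate r per year, the chance of one before first dose is 1 − exp(−r × days / 365.25).

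| Gap | r = 5% | r = 10% | r = 20% |
|---|---|---|---|
| 12 weeks (84 days) | 1.1% | 2.3% | 4.5% |
| 28 weeks (196 days) | 2.6% | 5.2% | 10.2% |
| 36 weeks (252 days) | 3.4% | 6.7% | 12.9% |

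If 10 to 25 Part 2 patients were formerly on placebo (also an assumption), the expected count per parameter runs from 10 × 1.1% = 0.1 to 25 × 10.2% = 2.5 patients. With same-day entry and r = 10%, it is 10 × 2.3% = 0.2 to 25 × 2.3% = 0.6. One patient in a 90-patient column is 1/90 = 1.1 percentage points.

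**Nearer sample.** Flow Chart footnote 2 provides for safety laboratory samples at the 1407-0030 end-of-treatment visit, with the tests not done there drawn at Visit 1. If Visit 1 is delayed, the full panel is drawn at Visit 1. Protocol 5.2.3 requires safety blood samples before dosing. A complete pre-dose panel is therefore planned for every Part 2 patient.

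**The case against.** **The laboratory sentence may mean first intake in this trial.** It names no trial, and the sentence after it speaks of first administration of trial treatment, a term SAP Table 6.1: 1 uses for dosing in 1407-0005. On that reading, Part 2 former placebo patients already have a Visit 1 baseline. The ambiguity is real, but this reading does not rescue the plan. It gives patients who were on active drug in 1407-0030 an on-drug baseline, which hides earlier drug-related shifts, and it contradicts the general rule in SAP 6.7 and protocol 7.3. The sentence needs rewriting either way.

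**One pre-randomisation baseline for everyone is a coherent, prespecified choice.** That is fair, and it is right for PASI. For laboratory shifts shown under a dose, it measures change since the start of the parent trial, which in former placebo patients is not change on drug.

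**The effect is narrow.** This stands. The Hy's Law plots use multiples of the upper limit of normal, and the abnormality counts use clinically significant ranges. Individual values are listed by visit, so timing can be recovered. There is no hypothesis testing.

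**Part 1 may contribute nobody.** A reader might take the 36-week gap as the headline, because protocol 3.2 says "Trial 1407-0005 may include placebo patients who have achieved a PASI 75 at Week 12 of 1407-0030 and a PASI50 at Week 24" and SAP 7.7 gives the example of "a Placebo patient that switches to BI 730357 100 mg at Week 12". The SAP does not support treating such patients as established. It was finalised in March 2021 and reports that all Part 1 patients were past 12 weeks when Part 2 enrolment began in December 2020. Its Part 1 adverse event columns and Week 24 efficacy groups contain no placebo group. Few or none may have entered.

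**Conclusion.** The point holds for Part 2 former placebo patients. On the natural reading of SAP 6.7, their laboratory baseline is about 12 weeks before first BI 730357 exposure, and up to 28 weeks with the maximum delay. The shift tables can therefore misstate change on 400 mg in both directions.

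The likely numerical effect is small: from a fraction of a patient to a few patients per parameter under the assumptions above. The true count cannot be derived, because the documents give neither the number of these patients nor a background rate of grade shifts.

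A reader might infer that the primary safety result is biased, or that every change on placebo is charged to the drug. Neither follows. The treatment-emergent adverse event rate does not use this baseline, and only changes that persist into an on-treatment sample are counted. The change is still worth making because it concerns patients newly exposed at the highest dose in the trial and costs little.

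**What to change.** In SAP 6.7, replace the laboratory sentence with a rule for the grade-shift and change-from-baseline tables: baseline is the last value before the first BI 730357 dose in either trial. In practice:

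- **On BI 730357 from the start of 1407-0030:** no change; the 1407-0030 baseline applies.
- **Part 2 former placebo:** the 1407-0030 end-of-treatment/Visit 1 sample, or the full Visit 1 panel if entry was delayed.
- **Part 1 former placebo, if any entered:** for period 2 only, the last value before the Week 12 switch. Use the Visit 1 value for HbA1c, lipids and infection tests, which are not drawn at Week 12. Keep the 1407-0030 baseline for period 1; otherwise the first-12-week values would have no earlier reference.

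Deleting the reference to placebo is not enough, because the general sentence would still apply. State the rule as an exception to it and record it in SAP section 4, which now declares no changes from the protocol. Keep the 1407-0030 baseline for PASI.

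The cost is a few SAP sentences and one derivation flag; no new samples are needed. The downside is that the baseline date then differs between former placebo and former active patients, which a table footnote should say.

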⁴Only applicable for women of childbearing potential. Urine pregnancy tests will be performed at all visits prior to administration of study drug. In case of a positive urine pregnancy test, a serum pregnancy test will be done. More frequent testing should be done if required by the local regulation or per investigator judgment.

C-SSRS 'since last visit' version used at all visits.

Whole blood Peripheral Blood Mononuclear Cell (PBMC) sampling should be taken approximately within 1 hour prior to administration of study drug.

¹⁰ Patients who discontinue trial treatment prematurely-should undergo the EOT visit as soon as possible and the End of Observation (EOO) Visit 4 weeks thereafter.

¹¹ Patients switching to licensed BI 730357 upon completion of active treatment in this study should not complete a washout period. Instead, their last trial visit will be EOT and trial completion will occur at that visit. These patients will not return for EOO Visit.

¹² Timing of the EOT visit is variable depending on when BI 730357 is approved and available on the market in the patient's country. Study visits (performing Visit 24 assessments and procedures) may continue every 12 weeks until licensed BI 730357 becomes available or the trial is terminated.

¹³ For patients who discontinue trial treatment prematurely, vital status will be collected once a year by telephone call starting from the last trial visit performed until the end of the originally planned observation period.

TABLE OF CONTENTS

TITLE PA	GE	1
CLINICA	L TRIAL PROTOCOL SYNOPSIS	2
FLOW CH	IART	5
TABLE O	F CONTENTS	10
ABBREVI	ATIONS	13
1.	INTRODUCTION	15
1.1	MEDICAL BACKGROUND	15
1.2	DRUG PROFILE	
1.3	RATIONALE FOR PERFORMING THE TRIAL	
1.4	BENEFIT - RISK ASSESSMENT	
2.	TRIAL OBJECTIVES AND ENDPOINTS	25
2.1	MAIN OBJECTIVES, PRIMARY AND SECONDARY ENDPOINTS	25
2.1.1	Main objectives	
2.1.2	Primary endpoint	
2.1.3	Secondary endpoints	25
3.	DESCRIPTION OF DESIGN AND TRIAL POPULATION	
3.1	OVERALL TRIAL DESIGN AND PLAN	26
3.2	DISCUSSION OF TRIAL DESIGN, INCLUDING THE CHOICE OF	• •
2.2	CONTROL GROUP(S) SELECTION OF TRIAL POPULATION	28
3.3 3.3.1		
3.3.2	Main diagnosis for trial entry Inclusion criteria	
3.3.3	Exclusion criteria	
3.3.4	Withdrawal of patients from treatment or assessments	
3.3.4.1	Discontinuation of trial treatment	
3.3.4.2	Withdrawal of consent to trial participation	
3.3.4.3	Williawai of conscit to that participation	
4	Discontinuation of the trial by the sponsor	
4.		32

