6.2.3 Follow up period and trial completion

For all randomised patients termination of trial medication and trial completion must be recorded on the corresponding eCRFs.

Early treatment and trial termination

If study medication is discontinued prior to the planned Flow Chart End of Treatment (EOT) Visit, the patient should undergo the EOT Visit as soon as possible and the End of Observation (EOO) Visit 4 weeks after last dose of study medication.

Vital status should be collected once a year by telephone call starting from the last trial visit performed until the end of the originally planned observation period.

Boehringer Ingelheim BI Trial No.: 1407-0005

06 Oct 2020

Clinical Trial Protocol

Trial completion

c22181693-04

Patients who finish the treatment period will return to the clinic for EOT Visit. Trial completion is defined as patients having reached the EOT visit within the specified window per the Flow Chart.

Patients switching to licensed BI 730357 upon completion of active treatment in this study should not complete a washout period. Instead, their last trial visit will be EOT and trial completion will occur at that visit. These patients will not return for EOO Visit.

Page 55 of 84

Page 56 of 84

Clinical Trial Protocol

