7.2 NULL AND ALTERNATIVE HYPOTHESES

There is no formal statistical hypothesis testing in this trial.

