7.4 PRIMARY ENDPOINT(S)

7.4.1 Primary analysis of the primary endpoint(s)

The primary endpoint is the occurrence of treatment emergent adverse events (TEAEs) up to Week 288. The primary analysis will be based on the exposure adjusted rate of patients reporting a treatment emergent adverse event (TEAE) up to Week 288.

Exposure-adjusted adverse event incidence rates will be calculated using the following approach:

- The incidence rate (per 100 subject years) of a selected adverse event (also known as the incidence density rate or person-time incidence rate) is defined as the number of subjects experiencing the adverse event per treatment group during the time at risk divided by the total time of subjects at risk in that treatment group to contribute an event to the analysis multiplied by 100 (per 100 subject years), where for each subject and each TEAE preferred term:

$$\text{Time at risk [subject years]} = (\text{date of first onset of AE} - \text{study drug start date} + 1) / 365.25$$

If, for a subject, no treatment emergent adverse event occurred for the preferred term, then the time at risk will be censored at the minimum of (date of death; drug stop date + 7 days; last contact date).

- For each AE, the incidence rate will therefore be calculated as:

$$\text{Incidence rate [per 100 subject years (pt-yrs)]} = 100 * \text{number of subjects with TEAE} / \text{Total TEAE-specific time at risk [subject years].}$$

Exact 95% confidence intervals (CI) around the observed AE incidence rate will also be provided using exact Poisson regression.

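### SAP 6.7 has no visit windows for treatment after Week 288 and SAP 7.4.1 sets no Week 288 limit on time at risk, although the protocol allows treatment to run longer

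*SAP*

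**What the plan says.** **Protocol.** Flow Chart footnote 12 states: "Timing of the EOT visit is variable depending on when BI 730357 is approved and available on the market in the patient's country". It adds that visits using the Visit 24 procedures "may continue every 12 weeks until licensed BI 730357 becomes available or the trial is terminated". Visit 24 includes vital signs, C-SSRS, PASI/sPGA and safety laboratory samples, so these further visits would produce data. For patients who move to licensed drug, section 6.2.3 says "their last trial visit will be EOT and trial completion will occur at that visit", and they have no end-of-observation (EOO) visit. The same section describes early termination with the words "If study medication is discontinued prior to the planned Flow Chart End of Treatment (EOT) Visit", and defines completion as reaching EOT inside its Flow Chart window, which is Week 288 ±7 days.

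**SAP 6.7.** Table 6.7: 1 has one EOT row (Week 288, nominal Day 2016, Days 1974 to 2029). The last row is EOS (Week 292, nominal Day 2044), which starts at Day 2030 and has no upper limit. The allocation rule is "On-treatment measurements for EOT and EOS visit for early discontinued patients will be allocated to visits by means of time windows". The SAP does not mention a variable EOT, patients switching to licensed drug, or visits after Week 288. SAP section 4 declares no changes from the protocol's analyses, so this is not a stated departure.

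**SAP 7.4.1.** The primary analysis is the "exposure adjusted rate of patients reporting a treatment emergent adverse event (TEAE) up to Week 288". The formula below it censors event-free patients at the earliest of death, drug stop + 7 days and last contact.

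**The concern.** The protocol allows treatment to last longer than the SAP's visit grid. Data from that extra time need a label and, for the primary rate, a rule on whether they count. The SAP gives neither.

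For the by-visit displays, the risk is that on-treatment values appear under a follow-up heading or under none, and that a Week 288 row contains values from other weeks. SAP 7.8.2 says that laboratory displays use these visit labels. SAP 6.7 picks one efficacy value per window, so if two treatment visits fall in the EOS window only one reaches the by-visit display.

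For the primary rate, the stated period and the computed period would differ for anyone treated past Week 288. The trial's stated purpose is long-term safety information to support registration, and the late rows are where that is shown.

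**Working it through.** **1. Reproduce the SAP's windows.** The rule is that the limit lies half-way between adjacent nominal days (7 × week) and the middle day goes to the later visit. At the end of the grid:
- Week 276 to Week 288: (1932 + 2016)/2 = 1974, so EOT starts on Day 1974.
- Week 288 to Week 292: (2016 + 2044)/2 = 2030, so EOT ends on Day 2029 and EOS starts on Day 2030.

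All 25 post-baseline windows in the table follow from this rule. The table is consistent with itself; it only ends too early.

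**2. Place the visits that footnote 12 allows.** With the ±7 days of Visit 24:
- Week 300: 7 × 300 = Day 2100, range 2093 to 2107.
- Week 312: 7 × 312 = Day 2184, range 2177 to 2191.

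Both lie wholly at or above Day 2030.

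**3. Apply the allocation rule under each reading.** The examples are illustrative, because the documents give no launch dates.

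| Case | Windows apply to all visits | Windows apply to early discontinuers only |
|---|---|---|
| Treatment visit at Week 300 or 312 | Labelled Week 292 / EOS | No label |
| Switcher's EOT at Week 180 (Day 1260) | In [1218, 1301], labelled Week 180: correct | If a completer, may keep the label Week 288, 288 − 180 = 108 weeks out; if an early discontinuer, labelled Week 180 |
| Switcher's EOT in Days 1974 to 2029 | Correct | Correct |

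Patients treated past Week 288 have no suitable label under either reading. Early switchers are affected only under the narrow reading, and only if 6.2.3 makes them completers.

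**4. Time at risk in the primary rate.** Assume first dose on Day 1, last dose on the nominal visit day, and no event of the term in question. SAP 7.4.1 then censors at drug stop + 7:
- Last dose at Week 300: 2100 + 7 = 2107 days. Excess over 2016 is 91 days, and 91/2016 = 4.5%.
- Last dose at Week 312: 2184 + 7 = 2191 days. Excess is 175 days, and 175/2016 = 8.7%.

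If events are stopped at Week 288 but time is not, the rate is too low. If both run on, the rate describes a longer period than the one stated, and the direction of the difference is unknown. If nobody were treated beyond Week 312, total time at risk could not grow by more than 8.7%, and it would grow by less the fewer patients pass Week 288.

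**5. Extend the grid by the SAP's own rule,** leaving EOS out of it:
- (2016 + 2100)/2 = 2058, so Week 288 becomes [1974, 2057].
- (2100 + 2184)/2 = 2142, so Week 300 becomes [2058, 2141].
- Later windows follow every 84 days.

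**The case against.** **Little depends on these labels.** Protocol 7.2 says "There is no formal statistical hypothesis testing in this trial". No endpoint is a visit value at Week 288. The Week 24 endpoints come long before the gap, time to loss of response is computed from visit dates, and on-/off-treatment status comes from dose dates in SAP Table 6.1: 1. With a protocol date of 05 Dec 2018, Day 2016 cannot occur before about June 2024, more than three years after the SAP of March 2021. All of this stands and keeps the impact modest.

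**The two labelling failures need different readings of one rule.** This also stands: they cannot both be asserted. The rule's wording limits it to early discontinuers, while the table's title and stated purpose suggest wider use. Section 6.2.3 could also make a patient who switches before Week 288 an early discontinuer, whose EOT would then be windowed correctly. The switcher problem is therefore conditional. The gap after Week 288 is not.

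**SAP 7.4.1 does name Week 288.** It does, in the sentence that defines the analysis. But the formula that would be programmed lists its censoring dates in full, and Week 288 is not among them. Protocol 7.3.4 has no such limit in its formula either.

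**Stronger readings that a reader might infer.**
- That off-drug and on-drug laboratory or PASI/sPGA values would be mixed under EOS. The Flow Chart schedules neither at EOO, so such values in that row would mostly be misplaced on-treatment data. Of the laboratory, vital-sign and PASI/sPGA displays, only vital signs have a scheduled EOO value to mix with.
- That 8% of treatment time and two scheduled visits per patient lie beyond Week 288. Six years is 6 × 365.25 = 2191.5 days, and (2191.5 − 2016)/2191.5 = 8.0%. But the protocol says only approximately six years, the Flow Chart schedules no treatment visit after Week 288, and footnote 12 says only that visits may continue.

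**Conclusion.** The point holds in a limited form. SAP 6.7 has no suitable label for on-treatment visits after Week 288, which the protocol allows. They go to Week 292 / EOS if the windows cover everyone, and to no row if they cover early discontinuers only. Whether a switcher's early EOT is labelled Week 288 depends on the reading of SAP 6.7 and on an ambiguity in protocol 6.2.3. Separately, the primary rate is defined to Week 288, but its censoring formula is not, so person-time, and possibly events, run past the stated period for anyone treated longer.

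The impact is limited to late by-visit displays (laboratory, vital signs, PASI/sPGA) and to the primary rate for patients treated beyond Week 288. The size cannot be given for the trial, because the numbers of such patients and of switchers are unknown. The figures of 91 days (4.5%) and 175 days (8.7%) are per-patient illustrations that assume last doses at Weeks 300 and 312. The conclusion rests on footnote 12 alone and does not need the six-year figure.

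**What to change.** In SAP 6.7:
- Assign every patient's EOT to a visit by day window, whatever the reason for ending treatment. This removes the dependence on how 6.2.3 classes switchers.
- Widen Week 288 to [1974, 2057], add Week 300 as [2058, 2141], and continue in 84-day windows for on-treatment visits. Adding Week 300 without widening Week 288 would leave Days 2030 to 2057 without an on-treatment window.
- Assign EOS only to the follow-up visit, by time since last dose (after last dose + 7 days), instead of from Day 2030 onward.

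In SAP 7.4.1:
- Add the Week 288 limit to both the event count and the censoring minimum for the primary rate. Give it as a day number, and say how the 7-day residual period is treated for a patient who stops at Week 288.
- Show the whole-treatment rate beside it, so that later safety data are not lost.

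The cost is a few lines of SAP wording, a small change to the visit derivation and one extra rate column. No new data are needed.
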